8.1.4 Dose titration

AFREZZA® should be taken at the beginning of the meal. An individualized postprandial dose will be administered 120 to 150 minutes after the initial dose if the SMBG exceeds 180 mg/dL. For dose titration, initial doses for lunch and dinner on Day 1 will also be determined based on the conversion table (Figure 1).

Throughout the study, doses for each of the following 3 days' meals will be titrated at the end of the current 3-day period based on the median SMBG (120 to 150 minutes post-dose) (Table 2). In other words, the subject will measure his/her 120 to 150 minute post-lunch SMBG for 3 days. The median dose (not the average dose, but the middle – between highest and lowest - of the 3 test values) will be used for dose adjustment per Table 2. This new dose should be used for the next 3 days. This process will be duplicated for both the post breakfast and dinner SMBG values.

Table 2 Recommended AFREZZA dose adjustments

Median 120-150 minute PPG value (mg/dL)	AFREZZA dose adjustment for that meal
<110	Decrease dose by 4 units
110-180	Maintain current dose
>180	Increase dose by 4 units

8.1.5 Postprandial dosing (follow-on doses)

If a subject's SMBG is greater than or equal to 180 mg/dL, 120 to 150 minutes after the prandial dose, the subject should take an additional, individualized postprandial or follow-on dose. The dose should be sufficient to reduce blood glucose below 120 mg/dL based on the subject's individualized dose-response.

8.1.6 Additional dosing of AFREZZA for snacks

Additional AFREZZA dosing may or may not be required with snacks. The need for a dose and the size of the dose depends on the size and content of the snack and the individual's dose-response.

8.1.7 Basal insulin dose adjustment

The basal insulin dose should be adjusted, as necessary, to achieve a fasting SMBG of 80 to 130 mg/dL.

8.2 NON-INVESTIGATIONAL MEDICINAL PRODUCTS

During the study, all subjects will receive daily injections of basal long-acting insulin.

8.3 METHOD OF ASSIGNING SUBJECTS TO TREATMENT GROUPS

In MKC-TI-155 Part 1, subjects will be assigned to their cohort based on their age.

8.4 PACKAGING AND LABELING

AFREZZA will be provided in 4, 8, and 12 unit cartridges with AFREZZA inhalers.

Empty AFREZZA cartridges are provided for training with the AFREZZA inhaler.

AFREZZA will be packaged and labeled per the FDA-approved prescribing information and for clinical trial use.

8.5 STORAGE CONDITIONS AND SHELF LIFE

AFREZZA should be refrigerated (2°C to 8°C or 36°F to 46°F). When in transit by a commercial carrier, the product may be shipped refrigerated or frozen (-25°C to -15°C or -13°F to 5°F). See Site Operations Manual for further information.

8.5.1 AFREZZA inhalation powder

When not in use: it should be stored in refrigerator at 2°C to 8°C (36°F to 46°F). Sealed (unopened) foil packages may be stored at 2°C to 8°C (36°F to 46°F) until the expiration date. **If a foil package is not refrigerated, the contents must be used within 10 days.**

When in use: it should be stored at room temperature at 25°C (77°F), excursions permitted to 15°C to 30°C (59°F to 86°F). Sealed (unopened) blister cards and strips must be used within 10 days, and **opened strips must be used within 3 days.**

8.5.2 AFREZZA inhaler

Store at 2°C to 25°C (36°F to 77°F): excursions permitted. Inhaler may be stored refrigerated, but should be at room temperature before use.

8.5.3 Handling

Before use, cartridges should be at room temperature for 10 minutes.

8.6 RESPONSIBILITIES

The Investigator, the clinical site pharmacist, or other personnel allowed to store and dispense investigational medicinal product (IMP) will be responsible for ensuring that the IMP used in the clinical study is securely maintained in a temperature-controlled environment as specified by the Sponsor.

All IMP shall be dispensed in accordance with the protocol, and it is the Investigator's responsibility to ensure that up to date and accurate records of IMP issued and returned are maintained.

Any IMP-related quality issues should be recorded and reported to the Sponsor by the means of a procedure on product technical complaint forms (refer to Site Operations Manual).

A potential defect in the quality of IMP provided by the Sponsor may initiate a recall procedure by the Sponsor. In this case, the Investigator will be responsible for promptly addressing any request made by the Sponsor to recall IMP and eliminate potential hazards.

Under no circumstances will the Investigator supply IMP provided by the Sponsor to a third party, allow the IMP provided by the Sponsor to be used other than as directed by this clinical study protocol, or dispose of IMP provided by the Sponsor in any other manner.

8.7 CONCOMITANT TREATMENT

A concomitant medication is any treatment used by the subject at the same time they are using the study IMP. Any treatment which is continued during the study and/or initiated or changed during the study must be recorded in source data and in the electronic case report form (e-CRF), including the name of the medication, indication for which the medication is being given, daily dosage, and duration of use.

During the study, all subjects will receive daily injections of basal long-acting insulin.

With the exception of ibuprofen and over the counter cold remedies, the use of any other concomitant medications (including herbal supplements) in the period from 2 weeks before the screening visit to the conclusion of the subject's participation in this study should be discussed with the Sponsor's medical monitor.

Subjects who have an intercurrent illness (including respiratory tract infections) will be treated at the discretion of the Investigator or a designee. After consultation with the Sponsor medical monitor, the subject may be discontinued from the study treatment.

During intercurrent illnesses, including upper respiratory tract infection, it is important that a subject's insulin be continued. At such times, more frequent monitoring of blood glucose concentrations and dose titration may be required. AFREZZA may be continued unless, in the judgment of the Investigator, temporary substitution with injectable insulin is needed.

Drugs or herbal preparations known to modify glucose metabolism, that may, in the opinion of the Investigator, interfere with the clinical study results should be discussed with the Sponsor's medical monitor. Dose adjustment and increased frequency of glucose monitoring may be required when AFREZZA is co-administered with drugs that may increase risk of hypoglycemia (ACE inhibitors, angiotensin II receptor blocking agents, disopyramide, fibrates, fluoxetine, monoamine oxidase inhibitors, pentoxyfylline, pramlintide, propoxyphene, salicylates, somatostatin analogs [e.g., octreotide], and sulfonamide antibiotics).

8.8 TREATMENT ACCOUNTABILITY AND COMPLIANCE

At each contact with the subject, either by telephone or during on-site visits, the Investigator or his/her delegate must ask the subject about administered doses of IMP and non-investigational medicinal product (NIMP).

Treatment units are returned by the subject at each on-site visit. The Investigator or delegate has to inspect IMP remaining in the returned packs and compare it to the dosing records documented in the subjects' diaries. Discrepancies have to be addressed with the subject for clarification of actual treatment administration. However, as subjects with T1DM require insulin, the level of glycemia as reflected by SMBG and HbA1c is a sensitive marker of adherence to insulin treatment.

The Investigator or delegate fills the treatment log form per subject and records the dosing information on the appropriate page(s) of the e-CRF.

The monitor will check the e-CRF data by comparing them with the subject's diary entries, treatment log forms, and unused treatment kits.

8.9 RETURN AND/OR DESTRUCTION OF TREATMENTS

Investigational medicinal product reconciliation must be performed at the site by the Investigator and the monitoring team using treatment log forms and documented on the center IMP inventory countersigned by the Investigator and the monitoring team.

A written authorization for destruction will be given by the clinical study team once the IMP reconciliation is achieved. This destruction can be performed at site depending on IMP specificities and local requirements or IMP can be returned to the Sponsor for destruction.

9 ASSESSMENT OF INVESTIGATIONAL MEDICINAL PRODUCT

All protocol-defined biological safety analysis, except SMBG, will be performed by a Central Laboratory. Detailed information on samples drawing, management, and analysis will be provided in a specific Central Lab Specifications (CLS).

9.1 PHARMACOKINETICS

All insulin PK parameters will be based on baseline-corrected insulin concentration. The baseline insulin concentration due to residual basal insulin will be estimated from the pre-dose blood samples. Insulin concentrations will be determined by validated radioimmunoassay. The FDKP serum levels will be determined by LC-MS and anti-insulin antibodies will be determined by radioimmunoprecipitation assay.

9.1.1 Sampling times

The sampling times for blood collection can be found in the Flow Chart [1.2](#).

9.1.2 Number of PK samples

The number of samples per subject and by study is indicated in [Table 3](#).

Table 3 Number of serum samples

	AFREZZA® insulin	FDKP	Anti-insulin antibody
By subject	14	5	2 ^a
Total for study (n subjects)	$14 \times 46 = 644$	$5 \times 46 = 230$	$2 \times 46 = 92$

a. Anti-insulin antibody samples to be collected at screening and end of treatment/early termination.

9.1.3 Sample handling procedure

The sample handling procedure is summarized in [Table 4](#).

Special procedures for collection, storage, and shipment will be provided in the CLS.

Table 4 Summary of handling procedures

	AFREZZA® Insulin	FDKP	Anti-insulin antibody
Blood sample volume	2 mL	2 mL	2 mL
Serum aliquot split	1 aliquot	1 aliquot	1 aliquot
Serum storage conditions	-70°C	-70°C	-20°C
Serum shipment conditions	Dry ice	Dry ice	Dry ice

9.1.4 Bioanalytical methods

A brief outline of the bioanalytical assay is provided in [Table 5](#) below.

Table 5 Summary of bioanalytical methods

Analyte	AFREZZA® Insulin	FDKP	Anti-insulin antibody
Matrix	Serum	Serum	Plasma
Analytical technique	Radioimmunoassay	LC-MS/MS	Radioimmunoprecipitation
Lower limit of quantification	8 µU/mL	1 ng/mL	NA
Assay volume	100 µL serum	200 µL serum	250 µL plasma

9.1.5 Pharmacokinetic parameters

The following PK parameters will be calculated, using non-compartmental methods using baseline-corrected serum insulin concentrations obtained after AFREZZA single dose. The parameters will include, but may not be limited to, the following:

- Insulin C_{\max} (maximum observed concentration after correction for baseline)
- Insulin $AUC_{0-\text{tlast}}$ (area under the baseline-corrected concentration-time curve from time 0 to the last measurable concentration)
- Insulin t_{\max} (time to reach C_{\max})
- Insulin AUC (area under the serum concentration versus time curve extrapolated to infinity) according to the following equation:

$$AUC = AUC_{\text{last}} + C_{\text{last}}/\lambda_z$$

- Apparent total body clearance (CL/F) and apparent volume of distribution (V_{ss}/F) calculated by standard non-compartmental methods
- Fumaryl diketopiperazine elimination half-life ($t_{1/2}$)

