4 INTRODUCTION AND RATIONALE

4.1 INTRODUCTION

In type 1 diabetes mellitus (T1DM), the therapeutic objective is to optimally control blood glucose levels and this objective is fundamentally the same in all subjects with T1DM. However, individual circumstances and needs dictate what those optimal levels should be. Children and adolescents with T1DM are dependent on insulin for survival (1), (2), (3), (4). Children and adolescents experience phases of growth and pubertal development associated with substantial changes in metabolism and, consequently, insulin requirements (5), (6).

AFREZZA® inhalation powder (hereafter referred to as AFREZZA®) consists of recombinant human insulin adsorbed onto fumaryl diketopiperazine (FDKP), a novel excipient which, at acidic pH, self-assembles into particles, and polysorbate 80. AFREZZA® is administered by oral inhalation using a breath-powered inhaler. AFREZZA® particles have a median diameter of approximately 2 to 2.5 μm , a size appropriate for inhalation into the lung. Following inhalation, AFREZZA® particles dissolve immediately at the physiologic pH of the lung, and insulin and FDKP are absorbed systemically.

AFREZZA® is currently available in cartridges labeled as “4 units”, “8 units”, and “12 units”. The actual contents are 10 units human insulin in a “4 unit cartridge”, 20 units in an “8 unit cartridge”, and 30 units in a “12 unit cartridge”.

AFREZZA® received Food and Drug Administration (FDA) approval for the treatment of adults 18 years or older with T1DM or type 2 diabetes. In subjects with T1DM, AFREZZA® must be used with a long-acting basal insulin formulation. After administration of AFREZZA® in adults, the maximum serum insulin concentration occurs in approximately 12 to 15 minutes (versus 45 to 60 minutes for rapid-acting analog [RAA] insulin via subcutaneous [SC] route) and returns to near baseline levels in approximately 180 minutes (versus about 5 hours for RAA) (7).

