6 STUDY DESIGN

6.1 DESCRIPTION OF THE PROTOCOL

MKC-TI-155 Part 1 will be a single-arm, multi-center, open-label, uncontrolled study to evaluate PK, safety, and ability to titrate AFREZZA® in children ages 4 to 17 years with T1DM, who were previously on a regimen of basal-bolus insulin therapy administered by MDI.

The structure of the study is as follows:

- Single dose PK at breakfast
- 4-week titration period starting at lunch after PK evaluation

On Day 1, subjects will receive a single dose of AFREZZA® prior to PK sampling. There will be 3 different doses of AFREZZA® for the PK study. The AFREZZA® dose (4, 8, or 12 units) will be based on the dose of SC RAA that the subject would usually receive with breakfast (Section 8.1.3). After this starting dose, each subject will be titrated with AFREZZA® TI according to the titration rules given.

The study will begin with Cohort 1 then proceed to Cohort 2 and Cohort 3 in parallel. Approximately 46 subjects will be enrolled into 3 age cohorts:

- **Cohort 1: 13 to 17 years;** approximately 18 subjects distributed across 4, 8, and 12 unit starting dose groups. Before proceeding to subsequent cohorts, at least 14 subjects must be dosed (i.e., complete PK Visit 2). Of those, at least 6 subjects must receive at least the 8 unit dose.
- **Cohort 2: 8 to 12 years;** approximately 14 subjects distributed across 4, 8 and 12 unit starting doses, as derived from the insulin:carb ratio – Figure 1. The sample size may be adapted after evaluating the PK data from Cohort 1.
- **Cohort 3: 4 to 7 years;** approximately 14 subjects will be treated and assessed for AFREZZA® distributed across 4, 8, and 12 unit starting doses, as derived from the insulin:carb ratio table – Figure 1.. The sample size may be adapted after evaluating the PK data from Cohort 1 and Cohort 2.

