8 STUDY TREATMENTS

8.1 INVESTIGATIONAL MEDICINAL PRODUCT

8.1.1 AFREZZA (Insulin Human) inhalation powder and inhaler

AFREZZA consists of single-use plastic cartridges filled with a white powder containing insulin, which is administered via oral inhalation using the AFREZZA Inhaler only.

AFREZZA Inhalation Powder is a dry powder supplied as 4, 8, or 12 unit cartridges.

The AFREZZA Inhaler is breath-powered by the subject. When the subject inhales through the device, the powder is aerosolized and delivered to the lung.

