Breakfast and AFREZZA dosing: subjects will receive a breakfast that is based on their assigned cohort and their Insulin/Carbohydrate ratio. (See Section 8.1.3 Initial dose for PK assessment) The meal will be provided by the clinical site. At the beginning of the meal, immediately before the first mouthful of food, the subject will inhale a dose of AFREZZA. The AFREZZA dose will be calculated based on the dosage table ([Figure 1](#)). The starting and ending time of breakfast will be recorded.

Post dosing assessment: the subject will then remain at the clinical study site for approximately 6 hours. The following procedures will be performed:

- 4-hour blood PK sample collection for insulin and FDKP. See [Table 3](#) for number of samples and [Flow Chart 1.2](#) for sampling times.
- Subjects will be monitored for signs of hypoglycemia. Blood glucose measurements will be taken during the course of the PK assessment visit according to the period [Flow Chart 1.2](#), preferably by table top glucose analyzers present in the Investigator's facility (e.g., Beckman or YSI). If blood glucose measurement cannot be done in the Investigator's facility, blood samples need to be sent for central laboratory measurement. A subject exhibiting signs of hypoglycemia will be treated as appropriate. A snack will be given (e.g., 6 oz of milk) if any glucose measured during the PK test is <75 mg/dL.
- Following the 4-hour PK test, plasma glucose will be assessed, after which the subject will receive another dose of AFREZZA, followed by lunch. The lunch should correspond in size and composition to the subject's usual lunch. The AFREZZA dose should correspond to the subject's usual dose of prandial insulin. Consideration should be given to adjusting the lunchtime AFREZZA dose based on plasma glucose readings during the PK test and the pre-lunch plasma glucose value.

Instructions for dose titration period

- The initial dose of AFREZZA for each meal will be determined based on the subject's usual RAA dose for those meals and the glucose profile during the PK test; the doses will be recorded on a subject reminder card that the subject will take with them.
- The subjects/parents will be instructed to administer AFREZZA at the beginning of each meal and to perform and record (e-Diary) an SMBG assessment at 120 to 150 minutes after each mealtime dose. Subjects will also be instructed to record the start and ending times of each meal and the AFREZZA® dosing time.

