4 STUDY ENDPOINTS AND COVARIATES

4.1 PK Endpoints

- Insulin C_{\max} (maximum observed concentration after correction for baseline)
- Insulin $AUC_{0-t_{\text{last}}}$ (area under the baseline-corrected concentration-time curve from time 0 to the last measurable concentration)
- Insulin t_{\max} (time to C_{\max})
- Insulin apparent clearance (CL/F)
- Insulin apparent volume of distribution (V_{ss}/F)
- Fumaryl diketopiperazine (FDKP) elimination half-life ($t_{1/2}$)
- Insulin AUC (area under the serum concentration versus time curve extrapolated to infinity according to the following equation:

$$AUC = AUC_{\text{last}} + C_{\text{last}}/\lambda_z$$

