Abbreviations: FEV ₁ , forced expiratory volume in 1 second; FDKP, fumaryl diketopiperazine; 
a. If the FPG value is ≥80 mg/dL at Visit 2, the subject will undergo a 4-hour PK assessment after eating his/her usual breakfast and receiving his/her breakfast dose of AFREZZA[®].
 
b. Glucose value via local or central laboratory: glucose reading to be done locally via a table top glucose meter (e.g., YSI) at Investigator site. Central laboratory will be used only if local reading (i.e., table top glucose meter) is not available.
 
c. Subject will inhale a dose of AFREZZA[®] under the supervision of the Investigator after the glucose sample has been taken and immediately before the first mouthful of food. The AFREZZA[®] dose will be calculated based on the conversion table. The AFREZZA[®] dosing time will be recorded in the electronic case report form (e-CRF).
 
d. Subject will receive a breakfast containing a predetermined level of carbohydrate, comprising approximately 50% of the total caloric content. The starting and ending time of breakfast will be recorded in the e-CRF.
 
e. At the conclusion of the PK test, plasma glucose concentration will be assessed and subjects will receive a lunch. The lunch should correspond in size and composition to the subject's usual lunch, and should be accompanied by an AFREZZA[®] dose corresponding to the subject's usual dose of prandial insulin with an adjustment (if necessary) based on the results of the glucose profile during the PK test and the pre-lunch plasma glucose value.
																				

PK parameters, as well as baseline-corrected insulin PK concentrations, will be computed by MannKind. The calculation methods will be described in a separate document (PK Analysis Plan for MKC-TI-155 Part 1).

The parameters will include, but may not be limited to, the following:

- Insulin C_{\max} (maximum observed concentration after correction for baseline)
- Insulin $AUC_{0-t_{\text{last}}}$ (area under the baseline-corrected concentration-time curve from time 0 to the last measurable concentration)
- Insulin t_{\max} (time to reach C_{\max})
- Apparent total body clearance (CL/F) and apparent volume of distribution (Vss/F) of insulin
- FDKP elimination half-life ($t_{1/2}$)
- Insulin AUC (area under the serum concentration versus time curve extrapolated to infinity) according to the following equation:

$$AUC = AUC_{\text{last}} + C_{\text{last}}/\lambda_z$$

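### Insulin Vss/F is a listed PK endpoint, but non-compartmental analysis of one inhaled dose without an intravenous reference cannot separate it from absorption time

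*Protocol*

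**What the plan says.** The volume appears in four places. The protocol synopsis lists it among the PK endpoints, and SAP 4.1 repeats it ("Insulin apparent volume of distribution", with the symbol Vss/F). Protocol 9.1.5 pairs it with CL/F, "calculated by standard non-compartmental methods". SAP 8.2 lists "Apparent total body clearance (CL/F) and apparent volume of distribution (Vss/F) of insulin" among the parameters to be computed and leaves the calculation methods to a separate PK Analysis Plan, which is not among the documents.

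The design supplies these data:

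- Dose: "On Day 1, subjects will receive a single dose of AFREZZA" (Protocol 6.1).
- Route: the powder is one "which is administered via oral inhalation using the AFREZZA Inhaler only" (Protocol 8.1.1).
- Reference: none. Part 1 "will be a single-arm, multi-center, open-label, uncontrolled study to evaluate PK" (Protocol 6.1), and the Day 1 schedule (Protocol 1.2) contains no intravenous insulin.
- Sampling: "4-hour blood PK sample collection for insulin and FDKP" (Protocol 12.1.2).

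Neither document gives a formula for Vss, MRT or mean absorption time. Neither lists Vz/F or an insulin half-life; the only half-life listed is for FDKP. SAP 8.2 has each PK parameter summarized by PK dose and cohort, with a 95% confidence interval for the geometric mean.

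**The concern.** Steady-state volume is clearance multiplied by the mean time that drug spends in the body once it has been absorbed. After inhalation, the serum curve reflects that time plus the time taken to be absorbed. The suffix /F allows for the unknown fraction absorbed; it does nothing about the time taken.

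The SAP introduction (1.1) states an aim of comparing PK with adults, and the data are meant to inform the age range and dosing of Part 2. Absorption from a breath-powered inhaler may differ between a young child and an adolescent. If so, the figure labelled Vss/F would differ between cohorts even if distribution did not. The insulin parameter summary (Table 14.2.2.1) is also marked for the DMC package in SAP Appendix 3.

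**Working it through.** **Step 1. The plan's own PK figure.** The documents give no figure for Vss/F. Their one quantitative PK statement is Protocol Table 6, on CL/F. With imprecision = 1 − exp(−t(0.975, n−1) × SD × √(χ²(0.80, n−1)/(n−1)) / √n), n = 14 and SD = 0.725:

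1 − exp(−2.160 × 0.725 × √(16.985/13) / √14) = 1 − exp(−0.4785) = 38.0%.

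This matches the table, and the other 24 entries also reproduce. The sizing on CL/F is sound and does not depend on what follows.

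**Step 2. The identity.** With linear disposition, after an extravascular dose:

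- AUMC/AUC = MRT_iv + MAT (AUMC is the area under the first-moment curve)
- Vss/F = (CL/F) × MRT_iv
- so (CL/F) × AUMC/AUC = (Vss/F) × (1 + MAT/MRT_iv)

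The factor is always above 1. CL/F = dose/AUC does not involve residence time and is unaffected.

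**Step 3. Why the factor cannot be identified.** In a one-compartment model with first-order absorption, C(t) is proportional to exp(−bt) − exp(−at), with a > b. Exchanging which rate is absorption and which is elimination changes only the scaling constant, and the unknown F and volume absorb that. Both readings give the same curve, the same AUC and the same CL/F, but different MRT_iv.

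**Step 4. Illustrative size.** Inputs:

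- Adult tmax of 12 to 15 minutes. Protocol 4.1 says "the maximum serum insulin concentration occurs in approximately 12 to 15 minutes".
- Return to near baseline in about 180 minutes (same section). The documents give no residual, so 2%, 5% and 10% of Cmax at 180 minutes are **assumed**.

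Solve ln(a/b)/(a − b) = tmax together with C(180)/C(tmax) = residual. Times are in minutes.

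| tmax | Residual | 1/a | 1/b | Total MRT | Factor, absorption fast (1 + b/a) | Factor, absorption slow (1 + a/b) |
|---|---|---|---|---|---|---|
| 12 | 2% | 5.0 | 41.6 | 46.6 | 1.12 | 9.36 |
| 12 | 5% | 4.4 | 54.6 | 58.9 | 1.08 | 13.47 |
| 12 | 10% | 3.9 | 71.2 | 75.1 | 1.05 | 19.23 |
| 15 | 2% | 7.1 | 40.2 | 47.3 | 1.18 | 6.63 |
| 15 | 5% | 6.2 | 52.9 | 59.1 | 1.12 | 9.58 |
| 15 | 10% | 5.4 | 69.2 | 74.6 | 1.08 | 13.74 |

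The trapezoidal rule on the nominal sampling times, with the terminal slope taken from the last three samples, gives nearly the same factors: 1.05 to 1.18 and 6.6 to 19.1. The sampling grid is not the problem.

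**Step 5. What Vz/F would and would not cure.** Vz/F = (CL/F)/λz can be computed from these samples. In the same model λz = b. If absorption is fast, Vz/F equals the true volume over F. If absorption is slow, it is too large by a/b, which is 5.6 to 18.2 (the last column minus 1). It is an honest label for a computable quantity, but it still needs a caveat.

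**The case against.** The strongest objection is that the calculation sits in a PK Analysis Plan that is not available here. That plan could compute (CL/F)/λz under a loose label, or bring in a mean absorption time from outside. A reader might infer that the trial will certainly report CL/F × MRT as Vss/F; the documents do not establish that. But either alternative would leave the protocol and SAP with the wrong label or an incomplete method, so a text correction is needed in every case.

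Second, the bias may be only 5% to 18%. That is correct if absorption is much faster than elimination, which the documents neither state nor test.

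Third, the consequence is limited. PK analysis is descriptive, the PK endpoints are not ranked, and no test, sample-size calculation or rule for opening the next cohort rests on Vss/F. This stands. Both parameter lists are also open-ended, so Vz/F, MRT or an insulin half-life can be reported without being added formally.

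Two stronger readings should be set aside:

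- *A tight confidence interval around the wrong quantity.* The documents point the other way. A cohort of 14 to 18 split over three starting doses gives about 5 or 6 per cell if even. At n = 6 and SD 0.725, Table 6 gives 60.1% imprecision for CL/F, which enters any such volume. The fault is where the interval is centred.
- *An overstatement above 20-fold.* A factor of 21 needs a 60-minute half-life (at tmax 13.5 minutes). That leaves about 15% of Cmax at 180 minutes, a poor fit to a return to near baseline by then.

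**Conclusion.** The point holds as a labelling and method defect. As written, standard non-compartmental analysis of a single inhaled dose does not yield the named endpoint. The product CL/F × MRT is too large by 1 + MAT/MRT_iv. The direction follows from the identity and needs only linear disposition; the size cannot be determined from these data.

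The ranges (about 1.05 to 1.18, or about 7 to 19) rest on a one-compartment model, adult timings and an assumed residual at 180 minutes. They show how far apart two readings of one curve can be and do not estimate the error in children. The practical risk is that a difference in absorption between age cohorts, or from adults, is read as a difference in distribution. How the value will actually be computed depends on the unseen PK Analysis Plan. The correction is worth making, but no main conclusion of the trial depends on it.

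**What to change.** - Remove Vss/F from the protocol synopsis, Protocol 9.1.5, SAP 4.1, SAP 8.2 and Table 14.2.2.1.
- Report instead Vz/F = (CL/F)/λz under that name, stating that it may be absorption-limited and is not to be read across ages as a distribution volume; and/or report MRT to infinity, labelled as including absorption.
- Add insulin apparent terminal half-life, ln 2/λz. The slope is already needed for the extrapolated AUC.
- Check the PK Analysis Plan and align it. If it already computes Vz/F, correct the label in the protocol and SAP. If it uses an external mean absorption time, state the source and amend the method.

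The cost is wording in the protocol, SAP and PK plan, and relabelled table rows. No extra samples are needed. The downside is that one listed PK endpoint is renamed or replaced.
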